Primary Specific Aim 2: Test the impact of dementia screening on the mood and anxiety symptoms of patient at baseline and 1, 6, and 12 months (i.e., primary potential harms).

(We hypothesize that screened subjects will not have higher depression or anxiety at one month post-screening (as measured by the Patient Health Questionnaire (PHQ-9) and Generalized Anxiety Disorder (GAD-7) scales)

Secondary Aims: Estimate the cost effectiveness of dementia screening.

(We hypothesize that screened subjects will have an Incremental Cost Effectiveness Ratio (ICER) below the maximum acceptable threshold of \$100,000 per quality adjusted life year saved at 12 months.)

B. Innovation

Pragmatic

Previous studies by our team and others have demonstrated that routine feedback of dementia screening scores, continuing medical education for dementia, and other passive educational interventions can improve rates of diagnosis, but not patient outcomes.^{12,28-32} We have shown that patients and families perceive potential harms from screening and that dementia screening can result in important incremental health care costs.^{21-23,33} Conversely, we and others have also already demonstrated that collaborative care, focused on non-

pharmacologic approaches to behavioral disturbances, can improve patient outcomes under experimental conditions.^{34,35} The innovation of this trial is in moving the process upstream to asymptomatic, older adults, cared for in typical but prepared community-based practices, to document actual benefits and harms, including costs. “Asymptomatic”, in the case of cognitive impairment, is paradoxical in some respects, but we denote asymptomatic to mean that the cognitive impairment is not a presenting symptom of the patient (just as hypertension is asymptomatic but can be detected by screening, cognitive impairment can be detected through screening tests).

Academic Community Partnership

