determine the subject's HRQOL.¹¹¹ The HUI is a generic, utility-based HRQOL instrument applied in patients with a wide range of medical conditions.^{111,112} It has eight attributes: Vision, hearing, speech, ambulation, dexterity, emotion, cognition and pain. The individual health domain scores range from 0.00 (maximum impairment) to 1.00 (no impairment) and the multi-attribute (HUI index) scores, a multiplicative function of individual attribute levels, range from 0.36 to 1.00 with anchors 0.00 = dead and 1.00 = perfect health. Naglie et al found that test-retest reliability exceeded the standard for adequate reliability of 0.70 in those with mild dementia (ICC = 0.75).¹¹³ [name] recently published a paper that provides new evidence regarding the construct validity (including responsiveness) of the HUI in community-based subjects with dementia.¹¹² The mean HUI multi-attribute utility score for 408 primary care patients with dementia was 0.54 (SD = 0.23) and the mean one year change was -0.30 among 240 dementia patients who remained in their own home after one year of receiving dementia care program whereas the mean one year change was -0.76 among 29 dementia patients who moved into a skilled nursing home facility.¹¹²

Mood and Anxiety Outcomes

We will use the **Patient Health Questionnaire–9 (PHQ-9)**¹¹⁴⁻¹¹⁶ and **Generalized Anxiety Disorder Scale (GAD-7)**^{117,118} to determine the impact of screening on our subjects' mood and anxiety at baseline, 1,6, and 12 months. We have used both instruments in various primary care-based research studies including our dementia collaborative care trial.^{34,51,93,114-118} The PHQ-9 is a nine-item depression scale with a total score from 0 to 27 and the GAD-7 is a seven-item anxiety scale with a total score from 0 to 21. Both of these scales are derived from the Patient Health Questionnaire; have good internal consistency and test–retest reliability; as well as convergent, construct, criterion, procedural and factorial validity for the diagnosis of major depression and general anxiety disorder.¹¹⁴⁻¹¹⁸ In our previous primary care studies, the mean

PHQ-9 scores ranged from 3.8 (SD = 5.1) to 4.4 (SD = 5.6) and the mean GAD scores ranged from 2.7 (SD = 3.2) to 3.2 (SD= 3.5).^{34,114-118}

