For any subject who expresses thoughts/tendencies of self-harm (a positive response of 1, 2, or 3 to question 9 on the PHQ-9), the Research Assistant will notify the Study Coordinator. The Study Coordinator will keep a detailed log of these events and will be responsible for notifying the subject's primary care provider immediately.

Health Care Utilization

We will obtain consent at enrollment from all subjects for permission to review their medical records. We will then use the Indiana Network for Patient Care (a fully operational Health Information Exchange) to identify any episode of ambulatory or acute care that occurred within the following 12 months of enrollment date. We will structure continuous variables that describe the number of ambulatory and/or acute care episodes. Furthermore, we will structure additional variables that describe a potentially preventable hospital admission (preventable hospitalization).⁷⁶ Preventable hospitalizations will include any hospitalization for an ICD-9 based disease that is considered an ambulatory care sensitive condition where the condition itself or its course can be mitigated through optimal outpatient management.

Other Data Collection

Social and Demographic

Patient age, gender, race, education, income, living situation, and marital status will be collected, along with social support as measured by the five-item Medical Outcome Study (MOS) social support instrument.¹¹⁹ The five-item MOS social support instrument was derived from the Medical Outcome Study (5 = worst to 25 = best). It has a minimum factor loading of 0.738 with Cronbach's alpha of 0.859.¹¹⁹ The five-item MOS instrument includes having

someone to confide in or talk to about problems, to get together with for relaxation, to help with daily chores if sick, to turn to for suggestions about how to manage personal problems, and to love and make feel wanted.^{119,120}

Common Chronic Conditions

Using the Indiana Network for Patient Care, we will evaluate all 4,000 subjects for the presence of ten common chronic diseases detected by ICD-9 codes in the year prior to enrollment: arthritis, congestive heart failure (CHF), coronary artery disease (CAD), cancer, chronic obstructive pulmonary disease (COPD), diabetes, stroke, hypertension, kidney disease, and liver disease. These conditions were chosen based on their high prevalence in our older adult population.^{33,47}

Medication Use

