Secondary Aim 1 compares depression and anxiety levels at 1 month post dementia screening between screened subjects and subjects in the no screening group. ANCOVA models will be used to compare PHQ-9 and GAD-7 obtained at 1 month between the screening and no screening groups adjusting for patients’ characteristics and baseline measures.

Secondary Aim 2 estimates the cost effectiveness of the dementia screening program in comparison to the “no screening”. This economic evaluation will be conducted from the societal and payer perspectives, including the direct medical care costs, caregiver and patient time and transportation costs, and the effect on quality of life for patients and caregivers.¹²³ Costs will be

divided into fixed and variable costs and by the screening, initial assessment phase and the follow-up phase of treatment. Total medical care utilization costs will be estimated for the control and screening groups from healthcare utilization and reimbursement data captured by the Indiana Network for Patient Care (INPC) during the trial. Prescription drug use will also be obtained from the INPC healthcare administrative database. The cost analysis will capture the extent to which screening, early diagnosis and coordinated care of patients with Alzheimer's disease affects medical care costs associated with dementia and co-morbid conditions such as diabetes, made worse by failure to manage dementia. Activity costing will be utilized to estimate the costs necessary to implement and operate the screening and collaborative dementia care management program and the usual care for dementia patients. Patient and caregiver time, staff time, fringe benefits, overhead costs, and materials will be logged by staff using the eMR-ABC software and assessed for the 12 month follow-up period. Included are waiting time, time with patients, time in meetings, lab services, telephone calls and mailings to participants. Excluded are costs associated with research. Transportation costs will be estimated from data on distance from home to clinic. Health care contacts will be dated and checked to avoid double counting via claims and activity costing methods.

Prescription drugs will be valued at the median wholesale price. A dispensing fee will be added for each 100 doses. Unit wage costs and fringe benefits will be standardized applying median values paid to personnel in the region; wage data collected from the health care system partners.

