ongoing care management). The latter (clinical data) will be managed using all the protocols that one would normally use with respect to usual clinical care and information protection procedures. Confidentiality with respect to research-obtained data will be protected using a logbook containing each participant's unique identification number, name, and status. This logbook will be maintained at the data management center of the Indiana University Center for Aging Research. The unique identifier will be kept separate from subject identifiers and will be stored with a unique but otherwise meaningless identification number. All data will be double keyed by a data-entry professional. All telephone-acquired data gathered by computer-assisted telephone interviewing (CATI) will be automatically entered in a data secure method and double keying will not be necessary due to immediate and error free method of data entry. In addition, for those in care management the principal investigators will have the opportunity for feedback from the patient and the clinic staff to discuss any problems encountered during the data collection.

M. Reporting of Unanticipated Problems & Adverse Events

A data safety monitoring board (**DSMB**) will be established and will include Drs. [name] (a neurologist), [name] (a geriatrician), [name] (a geriatric psychiatrist), and a biostatistician (TBN). The DSMB will be chaired by [name]. The committee will meet at the Indiana University Center for Aging Research prior to the first patient enrollment to determine the nature of the DSMB report, after enrollment of the first 1000 patients and every six months to evaluate safety measures including overall adverse effects related to the study (including the potential harms from screening such as anxiety, depression), serious adverse events, and death after enrollment into the study. In our study an adverse event will be defined as any untoward medical occurrence in a subject who received study intervention without regard to the possibility of a causal relationship. Adverse events will be collected after the subject has started to receive study intervention. If a subject experiences an adverse event after screening

for the study but prior to randomization, the event will be reported as not related to the study intervention. During the study, study personnel will note any change in the condition(s) and/or the occurrence and nature of any adverse events.

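### Positive answers to PHQ-9 item 9 are collected at every interview and logged, but no by-arm comparison is specified, so an excess of self-harm thoughts after screening could go unreported

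*Combined protocol and SAP*

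**What the plan says.** Under Primary Specific Aim 2 mood and anxiety are the trial's main potential harms, and the hypothesis is that "screened subjects will not have higher depression or anxiety at one month post-screening". Section H (Data Collection, Mood and Anxiety Outcomes) schedules the instruments to measure "mood and anxiety at baseline, 1,6, and 12 months" and describes the scale: "The PHQ-9 is a nine-item depression scale with a total score from 0 to 27".

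The same section sets the item 9 procedure. It applies "For any subject who expresses thoughts/tendencies of self-harm (a positive response of 1, 2, or 3 to question 9 on the PHQ-9"), and then: "The Study Coordinator will keep a detailed log of these events", and must also tell the subject's primary care provider at once. It is not limited to one arm. That both arms are covered is an inference from this wording and from the use of the PHQ-9 in all enrollees, but a safe one.

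Section I (Statistical Plan) lists the HUI, PHQ-9 and GAD-7 as the outcome measures. For mood it specifies one between-arm analysis, under Secondary Aim 1: "ANCOVA models will be used to compare PHQ-9 and GAD-7 obtained at 1 month". The power paragraph treats this as an equivalence question, with a margin of 0.6 (SD 5.1) on the PHQ-9. No section compares item 9 positives between arms.

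Section M has the DSMB "evaluate safety measures including overall adverse effects related to the study". It gives depression and anxiety as examples and adds serious adverse events and death. Item 9 and the log are not named. The board also meets before the first enrollment to decide what its report will contain. Section L (Potential risks) mentions suicidality only for case-by-case notification of medical personnel and the principal investigator.

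**The concern.** The trial asks whether the benefits of screening outweigh its harms, and its evidence on mood harm is a difference in mean PHQ-9 at one month. A mean is insensitive to an uncommon but serious event. If being screened, or being told of a positive screen, led a small fraction of subjects to report thoughts of self-harm, the mean would move little, and the trial could report no mood harm with that signal unexamined in its own data. A look at item 9 chosen after the results are known would carry less weight than one named in advance.

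**Working it through.** **Inputs from the documents.** N = 4,000, allocated 1:1; PHQ-9 margin 0.6 and SD 5.1; 10% missing at 12 months, giving 1,800 per arm. No loss is stated for 1 month, so 1,800 is the cautious choice. Item 9 scores 0 to 3.

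**Assumptions.** The documents give no item 9 rate, so rates are ranged. No equivalence test or level is stated; I use two one-sided tests at 5% each. The SD is unadjusted, as in the plan's power paragraph.

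**1. The plan's own figure.** SE = SD × √(2/n). Power at zero difference = 2Φ(margin/SE − 1.645) − 1.
- 2,000 per arm: SE = 5.1 × √(2/2000) = 0.161; 0.6/0.161 = 3.72; power = 96.2%. The GAD-7 (margin 0.5, SD 3.2) gives 99.9%. The stated figure of more than 95% reproduces.
- 1,800 per arm: SE = 0.170; 0.6/0.170 = 3.53; PHQ-9 power = 94.1%.

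**2. Effect of an item 9 excess on the mean.** Assume 3% positive in controls and 5% in screened subjects: 0.02 × 1,800 = 36 more people.
- Only item 9 changes, by 1 to 3 points: shift = 0.02 × 1 to 0.02 × 3 = 0.02 to 0.06, or 3% to 10% of the margin.
- Each extra case gains 10 total points: shift = 0.02 × 10 = 0.20, one third of the margin.
- Each extra case gains 15 total points: shift = 0.02 × 15 = 0.30, half the margin.

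**3. Chance of still declaring equivalence, 1,800 per arm.** P = Φ((0.6 − shift)/SE − 1.645) − Φ(1.645 − (0.6 + shift)/SE).

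| True shift in mean PHQ-9 | P(equivalence declared) |
|---|---|
| 0 | 94.1% |
| 0.02 | 93.9% |
| 0.06 | 92.5% |
| 0.20 | 75.9% |
| 0.30 | 54.8% |

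**4. Direct comparison of proportions.** Power = Φ((|p1 − p0| − 1.96 × SE0)/SE1), with SE0 pooled and SE1 unpooled; two-sided 5%, 1,800 per arm. For 3% against 5%, SE0 = 0.00653 and SE1 = 0.00652, so power = Φ((0.02 − 0.0128)/0.00652) = 86.5%.

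| Control rate | Screened rate | Power |
|---|---|---|
| 1% | 2% | 69% |
| 2% | 3.5% | 79% |
| 3% | 4% | 37% |
| 3% | 5% | 86% |
| 5% | 7.5% | 87% |

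At 3% against 5% the 95% CI for the risk difference is about ±1.96 × 0.00652 = ±1.3 percentage points.

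**The case against.** Several stronger readings are tempting, and the documents do not support them.

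- **That the DSMB would not see these events.** This cannot be inferred from silence. Section M lets the board set its own report, its list of safety measures is open-ended, and depression is on it. What stands is that nothing requires an item 9 count by arm.
- **That the information goes only to the primary care provider, or exists only in the log.** Section L also notifies the principal investigator when suicidality is apparent in a research interview. The item 9 answers are part of the PHQ-9 outcome data and enter the 1-month total in diluted form.
- **That equivalence would certainly be declared.** The 0.02 to 0.06 shift needs the other eight items to stay unchanged in people newly reporting self-harm thoughts, which sits badly with the good internal consistency that Section H claims for the scale. It is a floor. With larger gains per case the masking weakens: about 76% at 10 points and 55% at 15. It does not disappear.
- **That a direct comparison would reliably find the harm.** It would not for small excesses, as the 37% for 3% against 4% shows. The case for reporting it is the estimate and its interval, not a test.

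It can also be argued that a validated total is the proper outcome and an item-level result is a matter of preference. For a general mood outcome that is reasonable. It is less persuasive where the total carries the harm conclusion and the protocol already singles out this item for individual action.

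**Conclusion.** The concern holds as a gap in planned reporting. Item 9 responses are to be collected at four time points, and no between-arm use of them is specified beyond their share of the 1-month total score. Under an assumed 3% against 5%, equivalence would be declared with probability 92-94% if only item 9 moves and about 76% if each extra case gains 10 points, against 94% with no shift. A direct comparison has about 86% power in that case, and 37% to 87% over the rates examined.

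These figures rest on assumed item 9 rates, 1,800 per arm at 1 month, and two one-sided tests at 5%. They show what could be missed. They are not evidence that screening raises self-harm thoughts, and the gap does not invalidate the mean PHQ-9 comparison. The change is worth making because it bears directly on the harm conclusion and costs little.

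**What to change.** Add to Section I a descriptive harm outcome: item 9 positive (score 1 to 3) at the scheduled PHQ-9 interviews, in both arms. Report it by arm at 1, 6 and 12 months as number, percentage and risk difference with 95% CI, accounting for baseline item 9 status (for example, newly positive since baseline), beside the mean PHQ-9 result.

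Take the counts from the scheduled interviews, not from the coordinator's log or care-program contacts. As described, the log would also hold positives found at baseline, and program contacts arise only in the screening arm, so either source could distort the comparison.

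Propose the same by-arm count for the DSMB report when the board settles its content; Section M already has its members unblinded.

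The cost is one table and one line in the DSMB report, with no new data. The downside is a few extra descriptive estimates, to be read with their intervals and not as confirmatory tests. The notification procedure is unchanged.

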year. INPC also carries data from the Marion County Health Department; the Indiana State Department of Health; Indiana Medicaid; and RxHub, a national consortium of pharmacy benefit managers.⁴⁹ The INPC's rich clinical repository is organized by patient and medical record data and segregated into separate files by institutional source, but the data about one patient from many institutions can be viewed as a single virtual medical record, and clinicians can review a patient's record in a variety of video screens and hard-copy formats.

With initial focus in support of quality improvement, INPC is also beginning to serve biomedical research. In a recent clinical trial,^{34,51} we used INPC data to track utilization across the five health care systems in support of analyses examining the impact of new models of care on older adults health care utilization. These data were made available after appropriate approvals from the INPC Privacy Board which includes representative from all five health care systems and the Regenstrief Institute. Our study team has a track record in the responsible use of these data and in their appropriate data management and analysis.

Randomization

We will use a central, computer generated, web-based, randomization scheme to assign individual patients rather than providers or clinics to treatment conditions to minimize the effects of unmeasured case mix differences and clinic-level clustering. We estimate that the risk for 'spillover' from having participating clinics treat both intervention and usual care patients is likely to be small.^{34,51,72} If anything, patient-based randomization will conservatively bias the results in favor of usual care.

H. Data Collection (We will use face-to-face or telephone interviews for our data collections)

Health Related Quality of Life (HRQOL)

The primary outcome measure will be the HRQOL measured at baseline, 1, 6 and 12 months among the entire 4,000 enrollees. We will use the 15-item **Health Utility Index (HUI)** to

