Costs will be accumulated during the trial based on the probability of survival each month times the monthly cost of care for survivors to address censoring.¹²⁴ Effects and costs will be discounted at a 3% annual rate for the two-year trial period. The incremental CE ratio (ICER), will compare the no screening and less resource intensive usual care treatment strategy (UC) with the screening coupled with the more intensive treatment intervention (the

collaborative dementia care program) using the following formulas for (1) dementia patients (AP) and (2) Dementia patients plus their caregivers (CG).

$$ICER_{AP} = [COST_{HABC} - COST_{UC}] \div [QALY_{HABC} - QALY_{UC}] \quad (1)$$

$$ICER_{AP+CG} = [COST_{HABC} - COST_{UC}] \div [QALY_{HABC} - QALY_{UC}] \quad (2)$$

Uncertainty in the cost-effectiveness ratios and 95 percent confidence intervals will be assessed with 1,000 bootstrap samples. The outcome of each sample will be expressed as a scatter plot of incremental costs and effects generated from the bootstrap samples, reflecting the uncertainty arising from the model parameters. Results will also be displayed using net benefit analysis and cost-effectiveness acceptability curves (CEAC).¹²⁵ There is controversy about the appropriate ceiling ratio for health benefits.¹²⁶ Garber et al have recommended that a value of twice the median annual per capita income will result in efficient resource allocation.¹²⁶ The effects on ICERs of alternative unit cost estimates for care-giver time value and overhead cost rate for the screening and coordinated care management will be examined in a series of one-way and multi-way sensitivity analyses. The ceiling ratio λ will be varied from \$30,000 to \$150,000 per QALY for the CEAC analysis. The cost-effectiveness hypothesis will be tested against the \$100,000 per QALY maximum willingness to pay norm.

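### The cost-effectiveness analysis names no baseline adjustment for QALYs or cost, although baseline HUI and prior-year INPC records are within reach, and so gives up precision

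*Combined protocol and SAP*

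**What the plan says.** Section H (Health Care Utilization) uses INPC "to identify any episode of ambulatory or acute care that occurred within the following 12 months of enrollment date". Section I, Secondary Aim 2, takes medical cost from "healthcare utilization and reimbursement data captured by the Indiana Network for Patient Care (INPC) during the trial". Neither place defines a utilisation or cost variable for the period before enrolment.

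The same INPC source is nevertheless searched backwards. Section H (Common Chronic Conditions) evaluates all 4,000 subjects for the "presence of ten common chronic diseases detected by ICD-9 codes in the year prior to enrollment". For quality of life, section H states: "The primary outcome measure will be the HRQOL measured at baseline, 1, 6 and 12 months among the entire 4,000 enrollees".

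Section I specifies baseline adjustment for the 12-month HUI comparison (ANCOVA, followed by a mixed model with baseline covariates) and for PHQ-9 and GAD-7 at 1 month. For cost-effectiveness it gives two ICER formulas, one labelled for dementia patients and one for dementia patients plus caregivers. Each is a difference in cost divided by a difference in QALYs. The section adds discounting, survival weighting for censoring, net benefit and acceptability curves, and one-way and multi-way sensitivity analyses on caregiver time value and overhead rate. On uncertainty it says: "Uncertainty in the cost-effectiveness ratios and 95 percent confidence intervals will be assessed with 1,000 bootstrap samples". No covariate, regression or baseline-utility term appears.

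**The concern.** The HUI is baseline-adjusted when it is the primary outcome. No adjustment is named when the same HUI scores are turned into QALYs. If one arm starts with a slightly lower HUI, the ANCOVA removes most of that gap while a plain QALY difference keeps part of it. The trial could then report two quality-of-life differences that do not agree, for a reason unrelated to screening.

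The QALY difference is the ICER denominator, and it is expected to be small. Cost per person is usually skewed and varies widely between people, and prior-year use would normally explain part of that variation. The USD 100,000 per QALY hypothesis, for which the plan states no power, is therefore tested with less precision than the available data allow.

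**Working it through.** **The plan's own figure.** For 0.094 SD, two-sided alpha 0.05 and 80% power, n per arm = 2 × (1.960 + 0.842)² / 0.094² = 1,777, or 3,554 in total. Dividing by 0.90 gives 3,949 against the stated 3,951. With 1,800 per arm, the four table rows reproduce (77.9, 85.1, 86.4 and 91.0%). The primary sample size is not at issue. It fixes the number analysed: 2,000 × 0.90 = 1,800 per arm.

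**Inputs**
- HUI SD 0.23 (section H, from a dementia sample; assumed here for all subjects).
- Visits at 0, 1, 6 and 12 months (section H).
- Between-visit correlation ρ, the same for every pair of visits: 0.5 to 0.75 (assumed). The upper value is the test-retest ICC that section H cites for mild dementia.
- Correlation r between prior-year and trial-year INPC cost: 0.3 to 0.6 (assumed). The documents give neither r nor a cost SD.

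**QALY weights.** The trapezoid rule over 12 months gives w = 0.5/12, 3/12, 5.5/12 and 3/12, that is 0.042, 0.250, 0.458 and 0.250. The sum of squares is 0.337.

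**Formulas**
- Variance of the QALY in units of SD²: v = 0.337 + ρ(1 − 0.337).
- Slope of the QALY on baseline HUI: c = 0.042 + 0.958ρ.
- R² = c²/v.
- Raw SE = 0.23 × √v × √(2/1,800); adjusted SE = raw SE × √(1 − R²).

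| | ρ = 0.5 | ρ = 0.75 |
|---|---|---|
| v | 0.668 | 0.834 |
| c | 0.521 | 0.760 |
| R² | 0.41 | 0.69 |
| Raw SE of QALY difference | 0.0063 | 0.0070 |
| Adjusted SE | 0.0048 | 0.0039 |
| Reduction | 23% | 45% |

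The percentage reduction depends only on ρ and the visit schedule, not on the SD or the number per arm. The single-visit formula 1 − √(1 − ρ²) would give 13% to 34%. It understates the gain because a QALY averages several visits and includes the baseline visit itself.

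At USD 100,000 per QALY, the QALY part alone contributes a standard error of about USD 630 (raw) against USD 480 (adjusted) per person at ρ = 0.5, and USD 700 against USD 390 at ρ = 0.75.

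**What a baseline imbalance carries.** The SE of the chance baseline HUI difference is 0.23 × √(2/1,800) = 0.0077. A one-SE imbalance moves the raw QALY difference by 0.521 × 0.0077 = 0.0040 to 0.760 × 0.0077 = 0.0058. This is a component of the raw SE, not an addition to it: at ρ = 0.5, √(0.0048² + 0.0040²) = 0.0063. For scale only, the design effect is 0.094 × 0.23 = 0.0216, but that is a 12-month HUI difference and not a QALY.

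**Cost.** The SE is multiplied by √(1 − r²): 0.95, 0.87 and 0.80 at r = 0.3, 0.5 and 0.6, a reduction of 5%, 13% and 20%. No dollar figure can be derived from the documents.

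**Coverage.** In a simulation of one normal outcome (1,800 per arm, correlation 0.75, 2,000 replicates), normal-theory 95% intervals covered the truth in 94% of replicates for the raw difference and 95% for the adjusted one. The mean standard error was 0.033 SD raw and 0.022 SD adjusted.

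**The case against.** A reader might infer that chance imbalance biases the ICER or invalidates its interval. The documents do not support that. Patients are randomised individually by a central scheme (section G), so imbalance is sampling error. Resampling patients carries that error into the interval and the acceptability curve, and the coverage check above agrees. The cost is width, and a point estimate that ignores imbalance which can be seen.

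A reader might also infer that the plan commits itself to raw differences. It does not. The formulas are the generic definition of an ICER, an adjusted ICER is written the same way, and nothing rules adjustment out. This objection stands as to wording. It does not remove the point, because the plan spells out baseline terms for its other outcome comparisons, and leaving the choice open here allows it to be made after the results are seen.

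Two more objections stand in part. The ICER formulas are labelled for dementia patients, so a calculation on whole arms may not match the intended population. In a smaller subset the absolute errors would be larger, while the percentage gain at a given correlation would not change. Nor does every cost have a pre-enrolment counterpart: staff, patient and caregiver time logged in eMR-ABC and programme costs do not, and the prior-year search as planned yields disease flags rather than priced encounters.

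**Conclusion.** The point holds as a matter of efficiency and consistency, not of validity. Section I names no baseline adjustment for the cost-effectiveness result, although the needed baseline is collected (HUI) or reachable in a year of records already searched (INPC). Under the stated assumptions, adjusting for baseline HUI cuts the standard error of the QALY difference by about 23% to 45%. The 0.004 to 0.006 QALY carried by a one-SE baseline imbalance is part of that same error and should not be counted as a second harm. Adjusting INPC cost for prior-year cost cuts its standard error by about 5% to 20%.

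The absolute figures rest on an SD from dementia patients in a trial whose subjects are mostly not demented, and all reductions rest on assumed correlations. The QALY calculation also leaves out deaths, missing visits and discounting.

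**What to change.** In section I, Secondary Aim 2, state that within each bootstrap sample the incremental QALY is estimated by regression on arm and baseline HUI, and the incremental cost by regression on arm and prior-year INPC medical and drug cost or utilisation. Build the ICER, net benefit and acceptability curves from these estimates, and keep the unadjusted ICER as a sensitivity analysis. Say how the cost regression is combined with the planned monthly survival weighting.

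In section H (Health Care Utilization), extend the INPC utilisation extract to the 12 months before enrolment.

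Apply this to the patient ICER. The Overview of Data Sources table lists no caregiver baseline utility, so the caregiver ICER cannot be adjusted in the same way. eMR-ABC time and programme costs enter without a prior-year covariate.

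The HUI adjustment costs nothing beyond analysis code. The cost adjustment requires prior-year encounters to be extracted and priced, or counted if utilisation is used instead. Neither needs new patient contact.
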